### **MANAGEMENT OF NEW OR WORSENING PULMONARY SYMPTOMS**

If new or worsening unexplained pulmonary symptoms suggestive of pneumonitis (including, but not limited to, dyspnea) occur, or a deterioration of pulmonary function is observed, and/or radiologic abnormality is detected in the lungs, and this occurs in the absence of any clear diagnosis, a diagnostic workup (including high-resolution CT scan) in consultation with a

pulmonologist should be performed in order to rule out pneumonitis. During this time, treatment with study drug may be interrupted or continued per investigator discretion. If study drug is given in combination with another agent, the contribution of the other agent should also be assessed independently.

Following investigation, if pneumonitis is not confirmed, treatment with study drug may be resumed/continued as deemed appropriate by the investigator and in accordance with the study protocol directions for management of AEs. All confirmed events of pneumonitis should be treated as appropriate per medical judgement and institutional guidelines. If the event resolves and retreatment with study drug is being considered, please consult the study Medical Monitor. Retreatment with study drug may be resumed at the current or a reduced dose, if appropriate.

Refer to [Section 10.3](#) and [Section 10.8](#) of the protocol for additional information regarding classification and reporting of pneumonitis (and related events) as an AESI.

Dose reduction steps are presented in [Table 2](#).

Dose re-escalation upon resolution of toxicity to  $\leq$  CTCAE Grade 1 is permitted at the discretion of the investigator.

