**Table 3. Schedule of Assessments After Implementation of Amendment 5**

Procedure a	Blinded Treatment Phase (±3 days) Cycle X Day 1	Post-Treatment Phase		
		Treatment Discontinuation	28-day Follow-up	Long-term Follow-up
Adverse Events b	The investigator should monitor and educate patients on possible AEs observed with rucaparib		X	
Complete Blood Count	Monthly assessments advised			
Clinical Chemistry, Urinalysis, Vital Signs	Local standard of care practices per investigator			
Serum Pregnancy Test (WOCBP only) c	X	X		
Disease Assessment (Tumor Scans/CA-125) d	X e	X	X f	X f
Study Drug Dispensation/Administration/Accountability	X	X		
Tumor Tissue Biopsy (optional) g		X		
Subsequent Treatments, Secondary Malignancy Monitoring, and Overall Survival h			X	X

Abbreviations: AE = Adverse event; AESI = adverse event of special interest; CA-125 = cancer antigen 125; CR = complete response; CT = computed tomography; GCIG = Gynecologic Cancer InterGroup; MRI = magnetic resonance imaging; PET = positron emission tomography; RECIST = Response Evaluation Criteria in Solid Tumors; SAE = serious adverse event; WOCBP = women of child-bearing potential.

- a The study visit window in the double-blind treatment phase is ± 3 days, unless noted otherwise for a particular assessment. Study visits should take into account the subject’s investigational product supply. Study drug should be dispensed as applicable.
- b AEs will be monitored but only SAEs/AESIs are recorded through 28 days after last dose of rucaparib. Only treatment-related SAEs and all AESIs, regardless of causality, need to be reported after the 28-day window. Ongoing SAEs and AESIs will be followed until resolution, stabilization, or lost to follow-up.
- c Women of child-bearing potential must have a negative serum pregnancy test result ≤ 3 days prior to the first dose of study drug. A serum pregnancy test must also be performed ≤ 3 days prior to Day 1 of every cycle during the treatment phase and at the treatment discontinuation visit. All tests will be performed by a local laboratory.

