### **10.3 Definition of an Adverse Event of Special Interest**

An AESI (serious or nonserious) is one of scientific and medical concern specific to the sponsor's product or program, for which ongoing monitoring and rapid communication by the

investigator to the sponsor can be appropriate. Such an event might warrant further investigation in order to characterize and understand it. Depending on the nature of the event, rapid communication by the trial sponsor to other parties (eg, health authorities or ethics committees) might also be warranted.

Details on the sponsor's currently agreed list of AESIs for rucaparib can be found in the current rucaparib IB. These AESIs are to be reported to the sponsor expeditiously (see [Section 10.8](#) for reporting instructions).

Report any AE of pneumonitis, or any of the following AEs, irrespective of causality assessment and severity, as an AESI within 24 hours using the study Serious Adverse Event Form and the applicable procedures as outlined in Section 10.8:

- pneumonitis
- interstitial lung disease
- pulmonary fibrosis
- acute interstitial pneumonitis
- alveolitis necrotizing
- alveolitis
- hypersensitivity pneumonitis
- organizing pneumonia

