#### **11.2.5.1 Adverse Events**

AEs will be classified using the Medical Dictionary for Drug Regulatory Activities (MedDRA) classification system. The severity of the toxicities will be graded according to the NCI-CTCAE whenever possible. Only treatment-emergent adverse events (TEAEs) will be collected: TEAEs are defined as AEs with onset date on or after the date of first dose of study medication until the date of the last study medication dose plus 28 days.

The number and percentage of patients who experienced TEAEs for each system organ class (SOC) and preferred term will be presented. Multiple instances of the TEAE in each SOC and multiple occurrences of the same preferred term are counted only once per patient. The number and percentage of patients with at least one TEAE will also be summarized.

Separate tables will be presented as follows:

- All TEAEs
- TEAEs by CTCAE grade
- Grade 3 or greater TEAEs
- Serious TEAEs
- TEAEs with an outcome of death
- TEAEs leading to discontinuation of study medication
- TEAEs resulting in interruption/delay of study medication
- TEAEs resulting in dose reduction of study medication

If a patient experiences multiple occurrences of the same AE with different toxicity grades, the patient will be counted once for the maximum (most severe) toxicity grade. AEs with a missing toxicity grade will be presented in the summary table with a toxicity grade of "Missing." For each toxicity grade, the number and percentage of patients with at least one TEAE of the given grade will be summarized.

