3 GENERAL ANALYSIS CONVENTIONS

The summary tables will be presented by randomized treatment group (rucaparib vs placebo) within the nested populations outlined in the step-down procedure in Section 3.2 and other subgroups of interest.

Quantitative variables will typically be summarized using frequencies and percentages for appropriate categorizations and may also be summarized using descriptive statistics. For variables summarized with descriptive statistics, the following will be presented: N, mean, standard deviation, median, minimum, and maximum. Categorical variables will be presented using frequencies and percentages. The Kaplan-Meier methodology will be used to summarize time-to-event variables. If estimable, the 25th, 50th (median), and 75th percentiles will be presented along with the Kaplan-Meier estimates of event rates at 6-month intervals. The number of patients with events and the number of censored patients will also be presented. The stratified log rank test will be used to compare the PFS distributions between the randomized treatment groups. In addition, the Cox proportional hazards model will be used to estimate the hazard ratio between the randomized treatment groups. Months will be calculated as number of days divided by 30.4375.

All data will be used to their maximum possible extent, but without any imputations for missing data.

Unless otherwise indicated, baseline is defined as the last measurement on or prior to randomization.

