12.1 Adverse Events

AEs will be classified using the MedDRA version 19.1 classification system. The severity of the toxicities will be graded according to the National Cancer Institute Common Terminology Criteria for Adverse Events (NCI CTCAE) whenever possible. Treatment-emergent adverse events (TEAEs) are defined as AEs with onset date on or after the date of first dose of study medication until the date of the last study medication dose plus 28 days. AEs will be considered treatment-emergent if all or part of the date of onset of the adverse event is missing and it cannot be determined if the AE meets the definition for treatment-emergent.

The number and percentage of patients who experienced TEAEs for each SOC and PT will be presented. Multiple instances of the TEAE in each SOC and multiple occurrences of the same PT are counted only once per patient. The number and percentage of patients with at least one TEAE will also be summarized.

Separate tables will be presented as follows:

- All TEAEs;
- TEAEs by CTCAE grade;
- Grade 3 or greater TEAEs;
- Treatment-related TEAEs;
- Serious TEAEs;
- TEAEs with an outcome of death;
- TEAEs leading to discontinuation of study medication;
- TEAEs resulting in reduction study medication;
- TEAEs resulting in interruption of study medication;
- TEAEs resulting in reduction or interruption of study medication;
- Time to the first TEAE that results in a reduction or interruption of study drug.

The incidence of TEAEs will be summarized by relationship to study drug according to the following categories: "treatment-related," or "not treatment-related". If a patient experiences multiple occurrences of the same AE with different relationship categories, the patient will be counted once, as a relationship category of treatment related.

If a patient experiences multiple occurrences of the same AE with different toxicity grades, the patient will be counted once for the maximum (most severe) toxicity grade. AEs with a missing toxicity grade will be presented in the summary table with a toxicity grade of "Missing." For each toxicity grade, the number and percentage of patients with at least one TEAE of the given maximum grade will be summarized.

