The time to the first TEAE and first treatment-related TEAE that results in a dose reduction, delay, interruption, or discontinuation of study drug is defined as 1+ the number of days from the first dose of study drug to the start of the first adverse event. The cumulative incidence is presented in a 1-KM graph for just the patients with an event and the median time to onset will be calculated together with the 95% CI.

Non-TEAEs (pre-treatment and post-treatment) will be presented in the by patient data listings for the safety population.

MedDRA PTs were combined for the following similar terms:

- Asthenia/Fatigue
- Alanine Aminotransferase (ALT)/ Aspartate Aminotransferase (AST) Increased
- Anaemia and/or Low/Decreased Haemoglobin
- Thromobocytopenia and/or Low/Decreased Platelets
- Neutropenia and/or Low/Decreased Absolute Neutrophil Count (ANC)

In addition, the analysis of combined terms for anemia is explored as a time to first event analysis as described above. Transfusions (blood or plasma) and concomitant medications / growth factor support are provided in patient listings. The number of transfusions and the time to fist transfusion is also summarized.

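### The SAP gives no combined by-arm count for the eight pneumonitis-type AESI terms in protocol 10.3, and late-onset cases appear only in listings

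*SAP*

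**What the plan says.** **Protocol, collection.** Section 10.3 instructs sites: "Report any AE of pneumonitis, or any of the following AEs, irrespective of causality assessment and severity, as an AESI within 24 hours". The list has eight entries: pneumonitis itself, its acute interstitial and hypersensitivity forms, alveolitis and necrotizing alveolitis, interstitial lung disease, organizing pneumonia and pulmonary fibrosis. Section 7.4.2, on new or worsening pulmonary symptoms, points to 10.3 and 10.8 for the "classification and reporting of pneumonitis (and related events) as an AESI".

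**Tabulation.** Protocol 11.2.5.1 says "The number and percentage of patients who experienced TEAEs for each system organ class (SOC) and preferred term will be presented", and SAP 12.1 says the same: "The number and percentage of patients who experienced TEAEs for each SOC and PT will be presented". A patient counts once per class and once per preferred term. SAP 3 sets the layout: "The summary tables will be presented by randomized treatment group (rucaparib vs placebo". SAP 12.1 then states "MedDRA PTs were combined for the following similar terms" and names five groups: asthenia/fatigue, ALT/AST increase, anaemia, low platelets and low neutrophils. Neither SAP 12.1 nor protocol 11.2.5.1 lists an AESI table.

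**Time window.** Both documents close the treatment-emergent window 28 days after the last dose. For anything outside it, SAP 12.1 says "Non-TEAEs (pre-treatment and post-treatment) will be presented in the by patient data listings for the safety population". Protocol Table 3 keeps AESIs open beyond that point: "Only treatment-related SAEs and all AESIs, regardless of causality, need to be reported after the 28-day window". Protocol 10.7 and 10.8 repeat this.

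**Versions.** SAP 1 covers the original protocol and Amendments 1 to 3, the last dated 7 Jul 2016. The protocol at hand is the text after Amendment 5.

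**The concern.** The protocol's pulmonary section treats these terms as a family, with one work-up and one reporting route. The SAP accepts that similar preferred terms should be combined, and does so for five concepts, but not for the one concept for which the protocol spells out a term list.

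The quantity a safety reader would want is the number of patients per arm with at least one of the eight terms. No planned row supplies it. Splitting matters most for rare events, where each row may hold only one or two cases.

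Late events add a second gap. A case starting after the 28-day window must be reported to the sponsor, yet it enters no by-arm count at all, whether by single term or combined. The incidence of adverse events is a secondary endpoint (protocol Table 1), so this is part of what the trial set out to describe.

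**Working it through.** No figure in the plan bears on this, so there is nothing to reproduce. The check compares the lists and then gives a labelled illustration.

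**1. Overlap of the lists.** Protocol 10.3 terms: 8. SAP 12.1 combined groups: 5. Terms covered by a group: 0.

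**2. What the planned outputs give for one of these events.**

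| Output | Shown by arm? | What it counts |
|---|---|---|
| Preferred-term row | Yes | Patients with that one term |
| System organ class row | Yes | Patients with any event in the class, related or not |
| Combined row for the eight terms | Not planned | – |
| Onset later than last dose + 28 days | No | Patient listings only |

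The documents do not say which class or classes the eight terms fall in, so even the class row cannot be assumed to gather them all.

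**3. Why the rows cannot simply be added.** Let r1 to r8 be the preferred-term counts in one arm and n the number of distinct patients. Then max(r1,…,r8) ≤ n ≤ r1 + … + r8. The upper bound is reached only if no patient has two of the terms. The tables bound n but do not give it.

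**4. Illustration.** SAP 2.3 gives 540 patients at 2:1, so 540 × 2/3 = 360 rucaparib and 540 × 1/3 = 180 placebo. The incidences are assumed, because neither document gives one. For a row holding a share s of the cases, the expected count is N × p × s, and the arm difference is (p_R − p_P) × s. Each patient is taken to have one term.

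| Assumed incidence, rucaparib vs placebo | Combined row (s = 1) | Row with half the cases (s = 1/2) | Even split (s = 1/8) |
|---|---|---|---|
| 1% vs 0.5% | 3.6 vs 0.9 (0.5 points) | 1.8 vs 0.45 (0.25) | 0.45 vs 0.11 (0.06) |
| 2% vs 0.5% | 7.2 vs 0.9 (1.5) | 3.6 vs 0.45 (0.75) | 0.9 vs 0.11 (0.19) |
| 3% vs 1% | 10.8 vs 1.8 (2.0) | 5.4 vs 0.9 (1.0) | 1.35 vs 0.23 (0.25) |
| 5% vs 1% | 18.0 vs 1.8 (4.0) | 9.0 vs 0.9 (2.0) | 2.25 vs 0.23 (0.5) |

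For example, at 3% vs 1%: 360 × 0.03 = 10.8 and 180 × 0.01 = 1.8; divided by 8, 1.35 and 0.225. The even split is the extreme case. If nearly all cases code to the single term pneumonitis, that row comes close to the combined one.

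**5. Summary at study close.** After Amendment 5 only SAEs and AESIs are recorded on the adverse event form (protocol 10.7 and 13.6). The items that protocol 11.3 lists for summary at study close are all efficacy endpoints. No section names a summary of the AESIs collected in that period.

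**The case against.** - **A reader might infer that the arm difference in pneumonitis is never reported.** For on-treatment events the documents do not support that. SAP 3 and 12.1 together put every preferred term in by-arm tables, including the grade, Grade 3 or higher, serious, related, fatal and discontinuation tables where an event qualifies. Only the combined difference is missing. This objection stands. It does not reach events after the 28-day window, which have listings only.
- **A reader might also infer that the protocol defines one AESI group and the SAP dropped its analysis.** Protocol 10.3 is an expedited-reporting rule, and protocol 11.2.5.1 asks for no pooled row. Treating the eight terms as one concept is an inference, though a fair one given the wording in 7.4.2. No protocol-specified analysis has been lost.
- **The versions differ.** The SAP stops at Amendment 3, and nothing shows whether the eight-term list existed then. This stands: the gap may be a SAP not updated, rather than an oversight when it was written.
- **Part of the material is out of sight.** The full AESI list is in the Investigator's Brochure, and the content of SAP Appendices B and C cannot be read. A grouping there cannot be excluded, but section 12.1 points to none. The eight terms themselves are in the protocol, so this group can be specified now.
- **The size is assumed.** This stands. It would be wrong to say that the most visible row hides any particular share of the cases, because that depends entirely on how cases are coded.

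**Conclusion.** The point holds as a reporting gap of modest weight. The plan gives no by-arm count of patients with at least one of the eight terms, and the count cannot be recovered from the planned rows. For events starting after last dose plus 28 days, it gives no by-arm count of any kind, although those AESIs must still be reported.

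That the list and the pooling rule do not overlap is read directly from the documents. The size is not: the illustration rests on assumed incidences, about 360 and 180 patients, one term per patient and an assumed spread over terms. Across that range the combined difference is 0.5 to 4.0 percentage points, against 0.06 to 0.5 points in any one row of an even split. The documents do not show that the harm would in fact be understated. No primary or confirmatory efficacy result is affected.

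**What to change.** This changes tabulation only and leaves clinical management as it is.

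1. In SAP 12.1, add to the combined terms: 'Pneumonitis and related events (the eight terms of protocol 10.3)'.
2. Add a table by randomized arm, in the safety population, of patients with at least one such treatment-emergent event: any grade, and Grade 3 or higher. Count each patient once.
3. Add a separate by-arm count of such events starting after last dose plus 28 days, so that the treatment-emergent definition stays as it is.
4. Repeat both at the final analysis, and have the SAP state which protocol amendment it then covers.

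The data are already collected, so the cost is SAP wording and a small amount of programming.

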12.2 Clinical Laboratory Evaluations

Clinical laboratory evaluations include the continuous variables for hematology, serum chemistry, and urinalysis. The laboratory values will be presented in SI units. The on-treatment period will be defined as the time from randomization to 28 days after the last dose of study drug. Laboratory values collected during the on-treatment period will be included in the summary tables. The laboratory values collected after the on-treatment period will only be presented in the data listings.

The summary of laboratory data will include descriptive statistics (N, mean, SD, minimum, median, and maximum) of the maximum, minimum, and last value during the on-treatment period. Summaries using descriptive statistics of the change from baseline to the maximum, minimum, and last value during the on-treatment period will also be given.

Summary tables from baseline to the maximum on-treatment toxicity grade (CTCAE Version 4.03) for each lab parameter will be summarized. In addition, the number and percent of patients who has at least one worsening in toxicity grade on-treatment compared to baseline toxicity grade will be summarized by treatment group.

Laboratory data including normal ranges and flagged abnormal laboratory findings will be provided using by-patient listings.

12.3 Vital Signs

The on-treatment period will be defined as the time from randomization to 28 days after the last dose of study drug. Vital sign measurements collected during the on-treatment period will be included in the summary tables. The vital sign measurements collected after the on-treatment period will only be presented in the data listings.

The summary of vital sign data will include descriptive statistics (N, mean, SD, minimum, median, third quartile and maximum) of the maximum, minimum and last value during the on-treatment period. Summaries using descriptive statistics (N, mean, SD, minimum, median, and maximum) of the change from baseline to the maximum, minimum, and last value during the on-treatment period will also be given. The data will be presented separately for each randomized treatment group, and overall.

12.4 Examination of Safety in Subgroups

Safety will be further explored in the following subgroups:

- HRD subgroups per efficacy nested populations (tBRCA, HRD)
- tBRCA subgroups (germline, somatic)
- Age groups (< 65, 65-74, \geq 75)
- Race (white, non-white)

[figure not shown]

Appendix C
